## **2. INTRODUCTION**

This document describes the plan for the summarization and analysis of clinical data collected in Study 0171 for TD-9855, which was terminated early by the sponsor with 110 subjects enrolled.

### **3. STUDY OBJECTIVES AND ENDPOINTS**

#### **3.1. Objectives**

##### **3.1.1. Primary Objective**

The primary objective of the study is to evaluate the long-term safety of TD-9855 over a 182-week period.

[REDACTED]

#### **3.2. Endpoints**

##### **3.2.1. Primary Study Endpoints**

Primary safety and tolerability endpoints include:

- Physical examination
- Neurological examination
- Vital signs
- Resting ECGs
- Clinical laboratory tests including biochemistry, hematology, and urinalysis
- Concomitant medications
- AEs
- Subject compliance to study treatment
- Incidence of falls
- Columbia Suicide Severity Rating Scale (C-SSRS)

[REDACTED]

## 4. STUDY DESIGN

### 4.1. Summary of Study Design

[figure not shown]
This is a phase 3, multicenter, open-label study to evaluate the safety and tolerability of TD-9855 in subjects with primary autonomic failures (MSA, PD, and PAF) and symptomatic neurogenic orthostatic hypotension (snOH) over 182 weeks.

Subjects who complete Study 0170 will be eligible for this study. Following signing of the informed consent form, subjects will enter Study 0171 Visit 1, which will be conducted on the same day as Visit 9 of Study 0170.

[figure not shown]
Eligible subjects will receive a single dose of [REDACTED] TD-9855 [REDACTED] for 182 weeks.

A schematic representation of study visits is shown below:

#### Visits 1 to 6

#### Visits 7 to Telephone 8

Subjects may discontinue at any time. The stopping criteria include meeting at least one of the following conditions:

- A determination from the investigator that further administration of the investigational product may pose a safety concern to the subject
- Sustained (at least 4 hours) SBP > 180 mmHg or diastolic BP (DBP) > 110 mmHg after 3 min of standing or after 5 min in the sitting position, or a sustained (at least 4 hours) SBP > 180 mmHg or DBP > 110 mmHg measured in the supine state (head/torso elevated at approximately 30° from horizontal position)
- Intolerable AE as determined by the investigator
- Subject becomes pregnant

No dose reduction is permitted at any time.

Safety assessments for the first 26 weeks will include a physical examination, neurological examination, vital signs (HR, BP, respiratory rate, and body temperature), ECGs, safety laboratory tests (hematology, chemistry, and urinalysis), C-SSRS, and AEs. Safety assessments for the remaining 158 weeks will include evaluation of adverse events and concomitant medications.

The clinical assessments to be conducted are outlined in Section 4.5.

## 4.2. Study Drugs

The study drug will be TD-9855 supplied as a [REDACTED] tablet in 35-count high-density polyethylene bottles.

TD-9855 will be administered orally without regard to food at approximately the same time each morning and be taken with approximately 8 ounces of water.

Use of rescue medication during the study was discouraged, but midodrine was nonetheless provided as rescue medication, with the following restrictions:

- A maximum of 10 mg (increments of 2.5 mg are available) may be administered one day per week
- Cannot be used on assessment days

## 4.3. Sample Size Considerations

## 4.4. Randomization

Not applicable.

#### 4.5. Clinical Assessments

**Table 2: Schedule of Study Procedures (Visits 1 – 6)**

Each study visit for each subject may be conducted either in clinic or remotely									
Study Week (Visit/Telephone):	Week 0 Visit 1 (0170 Visit 9)	Week 2 Visit 2 +/- 3 days	Week 6 Visit 3 +/- 3 days	Week 10 Visit 4 +/- 7 days	Week 14 Telephone 1 +/- 3 days	Week 18 Visit 5 +/- 7 days	Week 22 Telephone 2 +/- 3 days	Week 26 Visit 6 +/- 7 days	Early Termination up to Week 26
Informed Consent	X								
Inclusion / exclusion criteria	X								
Medical history, including smoking history	X								
Concomitant Medications	X a	X	X	X	X	X	X	X	X
C-SSRS	X a	X	X	X		X		X	X
██████████	█	█	█	█		█		█	█
Vital signs (heart rate, blood pressure, respiratory rate, and body temperature)	X a, b	X b	X b	X b		X b		X b	X b
Physical examination	X a			X				X	X
Neurological examination	X a			X				X	X
12-lead electrocardiogram c	X a			X				X	X
Pregnancy Test	X a, c			X c				X c	X c
Safety Labs (chemistry, hematology, urinalysis)	X a			X				X	X
Dosing, Incidence of Falls, and Midodrine Diaries	X a	X	X	X		X		X	X
Adverse Events	X a	X	X	X	X	X	X	X	X

Each study visit for each subject may be conducted either in clinic or remotely									
Study Week (Visit/Telephone):	Week 0 Visit 1 (0170 Visit 9)	Week 2 Visit 2 +/- 3 day s	Week 6 Visit 3 +/- 3 day s	Week 10 Visit 4 +/- 7 days	Week 14 Telephone 1 +/- 3 days	Week 18 Visit 5 +/- 7 days	Week 22 Telephone 2 +/- 3 days	Week 26 Visit 6 +/- 7 days	Early Termination up to Week 26
Dispense Study Drug	X d	X d	X d	X d		X d		X d	
Study Drug Dosing	X d								
Collect Study Drug		X	X	X		X		X	X

- Study 0170 procedures conducted at Visit 9 will serve as the baseline assessment for Visit 1 of Study 0171.
- Vital signs will be assessed after the subject has been resting for at least 5 minutes in the seated or supine position.
- In women of childbearing potential only, urine beta human chorionic gonadotropin ( $\beta$ hCG) test will be performed and if positive, confirmation with serum  $\beta$ hCG test is required. The pregnancy test must be confirmed negative for a subject to be eligible for this study.
- Study drug will be ingested in the morning at approximately the same time of day with 8 ounces of water. The exact time and day of dosing will be recorded on the mornings of study visits. Subjects must be reminded to maintain an adequate fluid intake during their scheduled visits. Subjects will start taking study drug on the day after Visit 1.
- ECGs are done in triplicate after the subject has been resting for at least 5 minutes in a seated or supine position before the first reading, with each replicate separated by at least 1 minute.

**Table 3: Schedule of Study Procedures (Visits 7 – 14 Extension)**

Study Week (Visit/Telephone):	Wk 38 Visit 7 +/-7 days	Wk 50 Visit 8 +/-7 days	Wk 62 Telephone 3 +/-7 days	Wk 74 Visit 9 +/-7 day	Wk 86 Telephone 4 +/-7 days	Wk 98 Visit 10 +/-7 days	Wk 110 Telephone 5 +/-7 days	Wk 122 Visit 11 +/-7 days	Wk 134 Telephone 6 +/-7 days	Wk 146 Visit 12 +/-7 days	Wk 158 Telephone 7 +/-7 days	Wk 170 Visit 13 +/-7 days	Wk 182 Visit 14 End of Treatment Early Termination after Week 26 +/-7 days	Wk 184 Telephone 8 Follow-up +/-7 days
Procedure														
Concomitant Medications	X	X	X	X	X	X	X	X	X	X	X	X	X	X
Adverse Events	X	X	X	X	X	X	X	X	X	X	X	X	X	X
Pregnancy Test a		X		X		X		X		X			X	
Dispense Study Drug	X	X		X		X		X		X		X		
Study Drug Dosing	Xb													
Collect Study Drug	X	X		X		X		X		X		X	X	

a. In women of childbearing potential only, urine beta human chorionic gonadotropin (βhCG) test will be performed.

b. Study drug will be ingested in the morning at approximately the same time of day with 8 ounces of water.

## **5. TIMING OF PLANNED ANALYSES**

The primary analysis was to occur when all subjects had completed the [REDACTED] and the database had been cleaned and locked. A final analysis was to be conducted when all subjects had completed the study through Week 184.

The study was terminated early by the sponsor and a single analysis of all data obtained is to be conducted instead, after the database has been cleaned to the extent possible and locked.

## **6. CONSIDERATIONS FOR DATA ANALYSES AND HANDLING**

All data from scheduled and unscheduled visits will be presented in the subject listings.

However, unless noted otherwise, only data from visits (scheduled or unscheduled) that fall within the analysis windows will be included in summaries, statistical analyses, and calculation of derived variables. [REDACTED]

Analyses and tabulations will be prepared using [REDACTED]

Summary tables and listings will be prepared according to ICH Guideline E3 and will include a “footer” providing explanatory notes.

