### **6.3.10. Early Termination Up to Week 26**

Subjects terminating the study prior to Week 26 will complete all of the following procedures.

1. Review concomitant medications

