#### 6.4.3.9.4. Unscheduled Visit

All sites are allowed, at Investigator discretion, to conduct either in clinic or remote unscheduled visit(s) for subject safety or unexpected subject medical needs outside of the regular visit schedule. In this case, unscheduled visits are not considered protocol deviations and the Investigator is not required to obtain pre-approval from the Sponsor. Data collected during these visits may include any protocol-specified assessments which will be captured in the clinical database.

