### **6.3.5. Visit Windows**

All assessments will be summarized using analysis windows. The term “out of window” will be applied to assessments that are outside the analysis windows, regardless of the visit label associated with the assessment in the EDC system.

The following visit windows will be used in the summarization of clinical data:

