### **7.2. Subject Disposition and Completion Status**

The subject disposition summary will include the counts and percentages of subjects who:

- Completed study treatment
- Discontinued study treatment early, overall and by reason for not completing study treatment
- Completed the study
- Discontinued from the study early, overall and by reason for not completing the study

The subject disposition listing will include the date the informed consent form was signed, dates of first dose and last dose of study drug, primary reason for discontinuation of study treatment, and primary reason for study discontinuation. (If the treatment and study discontinuation reasons are the same for all subjects, as expected, a single column with the heading “Primary Reason for Discontinuation” may be shown.) A listing of premature discontinuation for reasons other than termination of the study by the sponsor will also be provided.

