#### 8.4. Laboratory Data

Laboratory data hematology and serum chemistry summaries will include summary statistics for observed values and for changes from baseline at each postdose visit. In addition, changes from baseline for each visit relative to normal ranges (e.g., shifts from normal to abnormal high/low) will be summarized in shift tables for hematology and serum chemistry test results. (Urinalysis data will be listed only.)

Listings will flag laboratory values that are outside the normal range.

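### On the readable text, Early Termination labs, ECGs and vital signs that fall between the SAP's analysis windows are listed but not counted in the safety category tables

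*SAP*

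**What the plan says.** SAP section 6 puts all scheduled and unscheduled data in the listings. For tables it then says that, unless noted otherwise, "only data from visits (scheduled or unscheduled) that fall within the analysis windows will be included in summaries". A redaction follows directly.

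SAP 6.3.5 applies the windows to all assessments and treats as out of window any "assessments that are outside the analysis windows, regardless of the visit label associated with the assessment in the EDC system". An ET label therefore does not bring a record back in. Table 4 lists Weeks 2, 6, 10, 14, 18, 22 and 26, each as its nominal day plus or minus 7. It has no ET row and nothing after Day 189.

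The SAP schedule gives ET its own column, headed "Early Termination up to Week 26", with vital signs, ECG and safety labs marked. Protocol 6.3.10 makes them mandatory: "Subjects terminating the study prior to Week 26 will complete all of the following procedures". Protocol 6.4.3.9.4 also allows unscheduled visits at any time: "Data collected during these visits may include any protocol-specified assessments which will be captured in the clinical database".

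The table descriptions in SAP 8.4 to 8.6 state no exception. Lab shifts cover "changes from baseline for each visit relative to normal ranges", and the Table 6 ECG categories are by visit. The vital-sign extreme-value summary and the normal/borderline/prolonged QTcF summary name no period, so the section 6 rule governs them. Falls, by contrast, have a continuous interval from Day 1 to Day 189 (SAP 8.7).

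**The concern.** Labs, vital signs and ECGs are primary safety endpoints, and the category tables are where a reader looks for how many subjects crossed a threshold. Readings taken when a subject stops early should not drop out of those counts because of the calendar day on which the visit fell.

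ET visits matter more than usual here. The SAP describes a study "which was terminated early by the sponsor with 110 subjects enrolled", and SAP 7.2 expects sponsor termination to be a common reason for stopping: "A listing of premature discontinuation for reasons other than termination of the study by the sponsor will also be provided". Any subject who had not reached Week 26 at that point was due the full ET assessment. The SAP was adapted to the termination elsewhere (one analysis instead of two, no subgroup summaries), but Table 4 gives ET records no place.

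**Working it through.** The plan states no coverage figure, so there is none to reproduce. The inputs are Table 4, the visit allowances and procedures in the SAP schedule (its Table 2), and SAP 6.3.1, where Day 1 is the first dose. Dosing is assumed to start the day after Visit 1, as planned.

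| Table 4 row | Window (days) | Gap before it | Protocol visit span | Vital signs due | Labs and ECG due |
|---|---|---|---|---|---|
| Week 2 | 7–21 | 1–6 | 14 ± 3 = 11–17 | yes | no |
| Week 6 | 35–49 | 22–34 | 42 ± 3 = 39–45 | yes | no |
| Week 10 | 63–77 | 50–62 | 70 ± 7 = 63–77 | yes | yes |
| Week 14 | 91–105 | 78–90 | telephone | no | no |
| Week 18 | 119–133 | 106–118 | 126 ± 7 = 119–133 | yes | no |
| Week 22 | 147–161 | 134–146 | telephone | no | no |
| Week 26 | 175–189 | 162–174 | 182 ± 7 = 175–189 | yes | yes |

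**Coverage.** Covered days = 7 × 15 = 105. Uncovered days = 189 − 105 = 84. The gaps agree: 6 + 6 × 13 = 84, and 84/189 = 44.4%.

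**On-schedule visits.** Every visit span lies inside its window, so visits made within their allowance are captured. The exposed records are ET assessments, unscheduled assessments, and visits made outside their allowance.

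**If tables show only weeks at which the assessment is due.** The SAP does not say whether an ET lab in, for example, the Week 6 window gets a Week 6 column in the lab tables. If it does not, fewer days lead to a count:
- Vital signs (Weeks 2, 6, 10, 18, 26): 189 − 5 × 15 = 114 days uncovered.
- Labs and ECG (Weeks 10, 26): 189 − 2 × 15 = 159 days uncovered.

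So 84 is the smallest number of uncovered days under either reading.

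**Stopping before Day 63.** The first scheduled post-baseline lab and ECG are at Week 10, which opens on Day 63. Apart from unscheduled tests, a subject with an ET assessment on Days 1–62 has only that one post-baseline lab set and ECG. The gaps before Day 63 are Days 1–6, 22–34 and 50–62. Take an ET visit on Day 55, with earlier visits on schedule: the Week 2 and Week 6 vital signs are counted, the ET vital signs are not, and the subject adds no post-baseline lab or ECG to any table.

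**Inside a window.** SAP 6.3.6 generally keeps the record closest to the nominal time. An extreme ET or unscheduled reading can therefore give way to a scheduled one in the same window. Contiguous windows alone would not solve this.

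**The case against.** **Redaction.** The rule in section 6 allows for exceptions and is followed at once by redacted text; text before section 10.2 is also redacted. Either could hold an ET or unscheduled-data rule. This stands: the point is conditional on the readable text.

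**The signal is not lost.** Clinically significant or symptomatic abnormalities are recorded as AEs if they meet the definition (Protocol 7.2), and the TEAE and AESI tables are not windowed. Listings flag out-of-range labs and extreme vital signs, and QTcF of at least 500 msec or a rise above 60 msec has its own listing. This reduces the loss. It does not replace a count, because threshold tables register a value whether or not an investigator judged it significant.

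**Is it a breach of Protocol 8.5?** A reader might infer so, but the documents do not support it. That section keeps unscheduled categorical findings out of by-time-point summaries and adds them only to summaries of the entire treatment period. It says only that unscheduled quantitative data are listed and not summarised. The readable SAP has no entire-period ECG category table from which such findings are missing. What can be said is that Protocol 8.5 foresees entire-treatment-period summaries that include unscheduled categorical findings, and the readable SAP has none for ECG categories.

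**Are 44% of readings or subjects lost?** That inference is also tempting and unsupported. The figure is a share of days. On-schedule visits are captured, and the documents do not say how many subjects stopped before Week 26 or when. Nor can the effect on a percentage be taken as one subject over 110: in by-visit tables an uncounted subject can leave the denominator too, as Protocol 8.5.6 provides for ECG.

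**Conclusion.** The point holds on the readable text. The window rule, the disregard of visit labels and the absence of an ET row together mean that an ET assessment in a gap is left out of the category tables for three primary safety endpoints. At least 84 of Days 1–189 are exposed in this way. The consequence is greatest for labs and ECG in subjects who stop before Day 63.

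The conclusion rests on two assumptions: that the redacted text holds no exception, and that dosing starts the day after Visit 1. The number of subjects affected cannot be derived from the documents. This is worth correcting before database lock. It is neither a protocol violation nor evidence that a safety signal would go unseen.

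**What to change.** Keep Table 4 for by-visit means, changes and shifts. In SAP 8.4 to 8.6 add, as a stated exception to section 6, an any/worst post-baseline row for the lab shift tables, the vital-sign thresholds (Table 5), the ECG categories (Table 6) and the normal/borderline/prolonged QTcF summary.

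- **Records:** all scheduled and ET readings from first dose to 14 days after last dose, matching the TEAE period in SAP 8.1. The documents set no interval between stopping and the ET visit, so state how a later ET reading is handled.
- **Unscheduled data:** include unscheduled ECG category findings, in line with Protocol 8.5. If unscheduled labs and vital signs are also included, state that this goes beyond Protocol 8.5. Protocol 8.1 allows such a change if it is pre-specified in the SAP before lock.
- **Denominator:** subjects with at least one post-baseline reading of that parameter, shown in the row.
- **Redacted text:** if it already has an ET or unscheduled-data rule, confirm that it covers these tables.

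The cost is SAP wording, a few table rows and some programming; no new data are needed. The drawback is that subjects with more readings have more chances of an extreme value, so the row should be read with its own denominator and not compared directly with single-visit rows.

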### **6.1. Analysis Sets**

#### **6.1.1. Enrolled Analysis Set**

The enrolled analysis set comprises all subjects who were enrolled into this study.

#### **6.1.2. Safety Analysis Set**

The safety analysis set comprises all enrolled subjects who received at least 1 dose of TD-9855 in this study.

#### **6.1.3. Examination of Subgroups**

The following subgroups were to be examined:

1. Disease type: MSA, PD, and PAF
2. Sex: Male and Female
3. Age category: < 65 years and  $\geq$  65 years
4. Smoking status: Never, Former, Current

But because the feeder study (Study 0170) was terminated early by the sponsor, the overall sample size is too small to warrant safety summaries by subgroup.

### **6.2. Baseline Definition**

In general, assessments obtained at Study 0170 Visit 9, which coincides with Study 0171 Visit 1, will serve as the baseline assessment for Study 0171. Subjects will start taking Study 0171 study drug on the day after Visit 1. If the start of Study 0171 dosing is delayed, however, the latest assessment obtained before the first Study 0171 dose will be used, even if obtained after Visit 1.

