### **4.1. Inclusion Criteria**

Subjects who meet the following criteria will be eligible for study enrollment:

1. Completion of Study 0170 and, in the opinion of the Investigator, would benefit from long-term treatment with TD-9855.
2. The subject must be able to understand the nature of the study and must provide written informed consent prior to the conduct of any study procedures (including any changes occurring in the subject's current therapeutic regimen).
3. The subject must be willing to continue on treatment and must continue to meet all the inclusion criteria for the preceding study (Study 0170) except, a score of  $\geq 4$  in OHSA#1.

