### **6.3.3. Change from Baseline**

Change from baseline is calculated as postbaseline result – baseline result. If either the baseline or the postbaseline result is missing, change values are treated as missing.

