### **7.5. Demographic and Baseline Clinical Characteristics**

A summary of demographic and baseline characteristics will include the following: age (years), age category (< 65 years, ≥ 65 years), sex, race, ethnicity, weight (kg), height (cm), BMI (kg/m^2), and diagnosis of primary autonomic failure (Multiple System Atrophy, Parkinson’s Disease, Pure Autonomic Failure). In addition, a summary of previous treatment during the Study 0170 randomized withdrawal period and a listing of previous treatment during the Study 0170 randomized withdrawal period and (if applicable) previous treatment during Study 0169 will be provided.

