#### 8.5. Vital Signs

Vital sign (HR, systolic and diastolic BP, respiratory rate, and body temperature) values and their changes from baseline at each visit will be summarized. If baseline BP and HR were collected as a part of the orthostatic standing test at Visit 9 (Day 155) in Study 0170, the seated values will be used to calculate the change from baseline. The counts and percentages of subjects with vital signs in the following categories will be presented in a vital signs extreme values summary. Extreme values will be flagged in the listing.

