## 8.6. 12-Lead Safety ECGs

ECG summaries will include summary statistics for observed values and changes from baseline. Heart rate and the following intervals will be included: PR, QRS, QT, and QTcF. A listing of 12-lead safety ECG data collected will be provided. A separate listing of data for subjects with postbaseline values of QTcF  $\geq 500$  msec or a QTcF increase from baseline  $> 60$  msec will also be provided.

In addition, QTcF (msec) will be summarized by the following categories: Normal (males  $< 430$ , females  $< 450$ ), Borderline (males  $[\geq 430, < 450]$ , females  $[\geq 450, < 470]$ ), and Prolonged (males  $\geq 450$ , females  $\geq 470$ ).

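### Pooled change-from-baseline safety summaries probably mix baselines taken on TD-9855 with baselines taken off it, and no visible text separates them

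*SAP*

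**What the plan says.** - **Baseline.** SAP 6.2 states, as a general rule, that "assessments obtained at Study 0170 Visit 9, which coincides with Study 0171 Visit 1, will serve as the baseline assessment for Study 0171". It adds that "Subjects will start taking Study 0171 study drug on the day after Visit 1". If dosing starts late, the latest pre-dose assessment replaces the Visit 9 value. Protocol 8.1 has a compatible rule: the last assessment before dosing.
- **Who enters.** Protocol 4.1 requires "Completion of Study 0170 and, in the opinion of the Investigator, would benefit from long-term treatment with TD-9855".
- **Where they come from.** SAP 7.5 plans "a summary of previous treatment during the Study 0170 randomized withdrawal period" and a by-subject listing of the same variable. This is the only visible use of it.
- **Change.** SAP 6.3.3: "Change from baseline is calculated as postbaseline result" minus baseline result. The formula is the same for everyone, and SAP 6.1.2 defines one safety set.
- **Where change is used.** For laboratory data (8.4), "changes from baseline for each visit relative to normal ranges (e.g., shifts from normal to abnormal high/low) will be summarized in shift tables"; these tables cover hematology and chemistry and stand next to summary statistics of change. For vital signs (8.5), "values and their changes from baseline at each visit will be summarized". For ECGs (8.6), "ECG summaries will include summary statistics for observed values and changes from baseline". Table 6 adds categories of change for HR, PR (percent) and QTcF, and a separate listing picks out subjects partly by a QTcF increase above 60 msec.
- **Subgroups.** SAP 6.1.3 drops safety summaries by disease type, sex, age and smoking because the sample is small. Previous treatment is not on that list.

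**The concern.** A randomized withdrawal period, with previous treatment worth summarising, implies that subjects differed in treatment as they left Study 0170. If that difference lasted to Visit 9, baseline means two things. For a subject who had been withdrawn, change from baseline is the change on re-starting TD-9855. For a subject who had continued, it is the change under continued treatment. The subtraction is well defined, but its meaning is not the same for all subjects.

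Vital signs, ECGs and laboratory tests are among the primary safety endpoints (SAP 3.2.1). The study has no control arm, so change from baseline is the main within-study contrast for them. A small pooled change in blood pressure, heart rate or QTcF could be read as no drug effect when part of it comes from baselines that already carried that effect. In a shift table, a subject already above range on drug at baseline cannot appear as a new shift. Likewise, the 60 msec criterion is harder to meet from an on-drug QTcF if the drug lengthens QTcF.

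SAP 8.5 does attend to comparability of baseline posture, by taking seated values from the orthostatic standing test. No similar provision for treatment state is visible.

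**Working it through.** The plan states no figure on this point, so there is none to reproduce. The check has a textual part and an illustration.

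**1. Text.** SAP 6.2, 6.1.2 and 6.3.3 give one baseline rule, one pooled set and one formula. SAP 7.5 gives a treatment variable from the preceding study. Sections 8.4 to 8.6 do not use it, and no redaction is visible within them. That some baselines were off drug is a strong inference, not a stated fact.

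**2. What depends on baseline.** Affected:
- laboratory, vital-sign and ECG change summaries;
- hematology and chemistry shift tables (urinalysis is listed only);
- the three change columns of Table 6;
- the 60 msec criterion of the QTcF listing.

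Not affected, because no baseline value is subtracted: observed values, Table 5, the absolute columns of Table 6, the normal/borderline/prolonged QTcF categories and TEAE counts. One rule may add to the mixing: SAP 10.2.4 replaces a missing laboratory baseline with the last available assessment, which could come from earlier in Study 0170.

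**3. Pooled mean.** Let p be the share off drug at baseline and D the off-to-on effect. Assume a steady effect and no residual drug at Visit 9. Expected change is D in the off-drug group and about 0 in the on-drug group, so

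pooled mean = p × D + (1 − p) × 0 = p × D.

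Residual drug at Visit 9 would reduce it further.

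**4. Precision.** N = 110 enrolled (SAP 2) is an upper bound. The SD of change, 10 units, is assumed. The 95% half-width is 1.96 × 10 / √n; for all 110 it is 1.96 × 10 / √110 = 1.9. The values of p are assumed.

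| p | n off / on | Pooled mean | Half-width off / on |
|---|---|---|---|
| 0.3 | 33 / 77 | 0.3 D | 3.4 / 2.2 |
| 0.5 | 55 / 55 | 0.5 D | 2.6 / 2.6 |
| 0.7 | 77 / 33 | 0.7 D | 2.2 / 3.4 |

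If only half the subjects have Week 26 data (assumed), p = 0.5 gives a half-width of 2.6 overall (n = 55) and 3.7 to 3.8 per column (n = 28 and 27).

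**5. Examples at p = 0.5, N = 110.** The pooled SD is √(100 + 0.25 × D²).
- D = 2: pooled mean 1.0, half-width 1.9. Negligible.
- D = 5: pooled mean 2.5, half-width 1.96 × 10.31 / √110 = 1.9. The off-drug column shows 5.0, half-width 2.6. Effect over standard error is 2.54 pooled and 3.71 in the off-drug column.
- D = 8: 4.0 pooled, 8.0 in the off-drug column.

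Ignoring the small between-group variance, the off-drug column's effect-to-standard-error ratio exceeds the pooled one by √(pN) × D / (p × D × √N) = 1/√p, which is 1.41 at p = 0.5. Under these assumptions, splitting does not lose the signal.

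**6. Shift table, simulated.** Assume 5% above range off drug, D = 0.5 SD and within-subject correlation 0.7. Normal-to-high shifts occur in 9.3% of subjects with off-drug baselines and 6.3% with on-drug baselines. Pooled at p = 0.5: 0.5 × 9.3 + 0.5 × 6.3 = 7.8%.

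**7. Amount of output.** Laboratory: 33 tests (17 hematology, 16 chemistry) × 2 visits = 66. Vital signs: 5 × 5 visits = 25. ECG: 5 × 2 visits = 10. Total 101 parameter-by-visit change summaries. A reduced set of SBP, DBP and HR at 5 visits plus QTcF at 2 is 15 + 2 = 17.

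**The case against.** The premise rests on one phrase in SAP 7.5. No visible text gives the comparator, the ratio, any washout, or whether the withdrawal period ran up to Visit 9. This stands: the sponsor must confirm treatment state before any table asserts it. A reader might infer that half the baselines were off drug; the documents do not support any particular share.

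The study is descriptive, and nothing says that pooled change estimates an off-to-on drug effect. This also stands, so it would go too far to call the analysis invalid or biased for a stated estimand. The problem is interpretation: a reader of the tables has no way to tell which kind of change is shown.

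Previous treatment will be listed, all visit data will be listed, and SAP 6 promises explanatory footers. The link could therefore be made by hand, but no visible summary makes it, and the footer content is unspecified.

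SAP 6.1.3 judged the sample too small for subgroup safety tables. That limits how far to split but does not settle the matter. The four factors dropped there are subject characteristics, whereas previous treatment determines what baseline is.

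Some text is redacted, including part of SAP 6 and of the protocol's statistical sections. A split could be described there, so the claim is only that none is visible.

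**Conclusion.** The concern holds as an interpretability problem with an inexpensive remedy. Mixed on-drug and off-drug baselines are probable, and the change-based outputs in SAP 8.4 to 8.6 pool them with no visible split or warning. With a steady effect and no residual drug, the pooled mean is the off-to-on effect times the share off drug at baseline: 50% at an assumed 1:1 split, and 30% to 70% over the assumed range. The share, SD, effects and correlation used above are all assumptions; the real size cannot be obtained from the documents and could be negligible.

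Two wider readings are not supported. The safety analysis as a whole is not compromised, because observed values, absolute thresholds and TEAE counts do not use a baseline value. Nor is Visit 9 the baseline without exception, since SAP 6.2 is a general rule with a delayed-dosing provision.

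**What to change.** 1. Have the sponsor confirm, from the Study 0170 design, each subject's treatment state at Visit 9.
2. In SAP 8.5 and 8.6, show change from baseline by Study 0170 randomized-withdrawal treatment plus a total column, at least for SBP, DBP, HR, QTcF and the three Table 6 change columns. Do the same for laboratory changes and shift tables (8.4) where numbers allow. Re-tabulating all 101 summaries is not required.
3. Add previous treatment to the listing of subjects with a QTcF increase above 60 msec.
4. Footnote the pooled change tables: *Baseline may have been on or off TD-9855, depending on Study 0170 treatment.*
5. State in SAP 6.1.3 that this descriptive split is separate from the four subgroups dropped there, because it defines the baseline condition.

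Cost: SAP wording and a grouping variable that 7.5 already summarises and lists. The split adds two columns to each table concerned, at least the 17 summaries counted above plus the Table 6 change columns. Numbers per column fall to about 55 each at an assumed 1:1 split of 110, before dropout. The total column is kept, so nothing now planned is lost. SAP 5 describes the single analysis as still to come after lock, and protocol 8.1 allows changes to be specified in the SAP before then.
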